# **Data Analysis**

Primary outcome: The primary outcome (attendance to follow-up appointment with a glaucoma specialist within three months) will be summarized with frequencies and percentages by intervention and control groups, overall and stratified by site.

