Aim 3: (Phase 2- HUM 00169371) Integrate personalized glaucoma education and counseling during the technician visit and test the behavioral intervention's impact on adherence to follow-up care with an ophthalmologist. We hypothesize that personalized eHealth education and motivational-interviewing-based counseling will improve adherence to glaucoma follow-up care compared to standard education delivered by a trained staff member. We will test our hypothesis in a randomized controlled trial with participants (n=400) from Aim 2 who have glaucoma or suspected glaucoma. We will make iterative refinements to our existing evidence-based, individualized counseling/eHealth glaucoma education program with a focus on adherence to follow-up recommendations based on learning in Aim 1. The primary outcome is the proportion of participants attending the recommended physician appointments within three months. Secondary outcomes include glaucoma knowledge, satisfaction with communication, and confidence in asking the ophthalmologist questions. Program economic efficiency will be assessed.

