**Baseline Surveys**: For surveys, ophthalmic technicians will administer the National Eye Institute Visual Function Questionnaire – 9 to patients, which assesses vision-related quality of life. Additional surveys will include: Flint Water- questions are related to living in Flint during the water crisis, Everyday Discrimination Scale, Perceived Stress Scale, UCLA Loneliness Survey, Fall history and Timed Up & Go. They will also administer a standardized survey about socio-demographics and health history. Patients will confirm their address, phone number, and contacts in case of an emergency.

Eyeglasses: After the examination, ophthalmic technicians will help participants who need correction select free (ReSpectacle.org) or low-cost (ZenniOptical.com) eyeglass frames. ReSpectacle.org are donated glasses that have been categorized by exact prescription and are viewable on the website. The organization ships the glasses free- of charge. Participants may also purchase low cost (\$10-\$50) glasses on ZenniOptical.com. On this website, people can choose the frames. For both options, technicians will place the on-line order after the ophthalmologist confirms the eyeglasses prescription remotely, glasses will be shipped to the clinic.

Physician Evaluation: Physician's evaluation will be via a store-and-forward telemedicine technique. This store-and-forward technique, or asynchronous telemedicine, involves the electronic transmission of health data to the provider for evaluation and management. Physicians will review data received within 1 week. The reading ophthalmologist will enter the data into the UM EHR (MiChart). The physician will complete one of two letters with the examination results for the participant indicating whether the participant has ophthalmic disease or not. A time frame for an in-person ophthalmologist examination will be requested if needed. This letter will be sent to the patient via mail and the technician and the patient's PCP (if they have one) via the EHR.

**Physician Review Glaucoma Screen:** In terms of glaucoma screening, a "positive screen" for glaucoma or glaucoma suspect will include the following exam criteria as defined by the TECS protocol:

- 1) Cup to disc ratio  $\geq 0.7$
- 2) Intraocular pressure ≥ 21 mm Hg
- 3) Disc hemorrhage
- 4) Asymmetry of the cup-to-disc ratio by  $\ge 0.2$  where the larger cup-to-disc ratio is  $\ge 0.6$
- 5) Rim thinning or focal notch

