- 6) Abnormal retinal nerve fiber layer observed on OCT defined as >10 microns difference in average retinal nerve fiber layer between the two eyes or the presence of thinning (defined as <5% or yellow) in any of the superior or inferior clock hours)
- 7) Narrow angles on penlight examination or any other concern for narrow angle (complaint of chronic headache or red eye)
- 9) Afferent pupillary defect
- 10) Patient already on treatment or being followed for glaucoma

Physicians will also evaluate for diabetic retinopathy and macular degeneration using validated TECS protocols. If the ophthalmologist identifies an urgent issue such as corneal ulcer, optic disc edema, melanoma, tumor, or retinal vascular event (e.g. central or branch retinal vein or retinal artery occlusion), the physician will contact the patient by phone to arrange immediate care.

Follow-up: The technician will schedule a follow-up visit 4-8 weeks later to give participants their eyeglasses and adjust them. Participants that do not need eyeglasses, but screen positive for eye disease, will return to review their diagnosis letter and management plan and help the patient to schedule an in-person appointment with the ophthalmologist. The ophthalmic technician will help the patient arrange follow-up care and provide educational material to explain diagnoses of cataract, diabetic retinopathy, macular degeneration or glaucoma. (UM Health System Patient Education Clearinghouse at https://pteducation.med.umich.edu/kellogg) If the participant has no need for eyeglasses and has no eye disease, the technician will call the participant to cancel the follow-up appointment after reviewing the ophthalmologist's recommendations. During the follow-up phone call, the satisfaction survey will be administered that would have otherwise been administered at the follow-up visit.

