Glaucoma or glaucoma suspect: Patients with a diagnosis of glaucoma or glaucoma suspect who speak English will be randomized (1:1) to receive standard care as described above, or a 60-minute personalized counseling and education program (intervention) about their diagnosis and the importance of glaucoma follow-up care in maintaining vision (Aim 3)). Ocular hypertension that is low risk for developing glaucoma within one year and/or the recommended follow up time period is one year or more, will not be randomized, the PI will review these cases to determine if they should be randomized or not. Randomization will occur in web-based randomization system. Both groups will be provided support scheduling their ophthalmologist exam and will be asked to complete a brief satisfaction survey. The standard care group will receive a reminder call prior to the ophthalmologist exam, while the intervention will receive a

reminder call as well as a 10-15 minute motivational-interviewing based- counseling follow-up phone call to remind them of why following up for glaucoma care is important to them and trouble-shoot barriers to attending. Further discussion regarding personalized counseling and motivational interviewing can be found later in this protocol. All non-English speaking patients will not be randomized and will receive standard of care education; the personalized counseling is only available in English. We have created a Spanish version of the personalized counseling. Spanish speaking participants will not be randomized, all will receive the personalized coaching session. A Spanish speaking study coordinator will conduct the Spanish eHealth coaching. All subjects participating in the counseling/education encounters will have the option to have their sessions be audio-recorded. Additionally, we will ask English and Spanish speaking participants to complete a visual field test at this appointment. A visual field test measures peripheral vision and is used to review glaucoma patients. This test will take about 20 minutes and there will be no charge to the participant or their insurance. Visual field data will be entered into the REDCap database.

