## **Research design-Intervention**

Block randomization: Subjects will be randomized to one of two treatment arms (standard glaucoma education from handouts or personalized education with counseling) in a 1:1 ratio. The time of randomization is when the patient returns for their follow-up visit with the ophthalmic technician. Randomization will occur separately for the two clinics (stratification). A variable-block randomization scheme will be used to assure balanced assignment to the treatment arms throughout the study.

Leveraging eHealth to provide personalized glaucoma education and counseling: The web-based application for personalized glaucoma education has two components woven together into a single tool to support the conversation between the patient and the glaucoma

counselor: 1) an electronic health (eHealth) component and 2) a semi-structured, tailored interview guide to facilitate an MI-based conversation. The eHealth component provides individually tailored disease information and an explanation of a patient's test results. The counselor uses the web-based application on a tablet, to share engaging audio-visual content on a screen. The counselor walks a patient through their diagnosis and test results and what would happen to their vision if glaucoma goes untreated. The counselor then elicits an understanding of what motivates that patient to maintain their vision. The counselor explores what unique obstacles the patient has to engaging in follow-up care. The counselor then assesses the patient's motivation to attend the follow-up appointment. The counselor and patient create a concrete "action plan" that delineates the short-term plan of the steps patient will take to address any identified barriers to follow-up care, which can include addressing motivational factors in a subsequent phone visit if a patient is not interested in follow-up care.

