During the first day of training, counselors are taught to ask open-ended questions, or questions that cannot be answered with a "yes" or "no" response. They learn reflective listening, or para-phrasing what a person has said to ensure the person knows the counselor

is hearing and understanding what they say. They learn to use affirmations to praise actions people are taking towards improving their health and vision. They learn to use the elicit-provide-elicit technique to give information. This involves assessing people's knowledge prior to giving information, asking permission to give new information or advice, and then following up by eliciting the person's response to the new information in order to evaluate their understanding. This non-directive way of giving advice and information supports people's autonomy. During the second day of training, counselors are taught how to make complex reflections.

Complex reflections are statements that para-phrase what a person has said and adds significant meaning to help make a person think about the implications of their statement. Counselors learn how to promote change talk and develop an action plan to adhere to follow-up care recommendations.

Role playing is used to develop these skills using a video collection of glaucoma patients explaining their reasons for not engaging in their glaucoma management. The training consists of approximately 35% didactic material and 65% role-playing and interactive learning.

Primary outcome: The primary outcome will be adherence to the recommended follow-up appointment with the ophthalmologist within 6 months due to availability in scheduling these appointments. Six-month adherence will be used as the endpoint for all participants. Adherence in each treatment group will be calculated as the proportion of patients who attended the initial scheduled follow-up visit with an ophthalmologist as recommended after being diagnosed with glaucoma or glaucoma suspect on screening exam, dividing by the total number of patients diagnosed with glaucoma or glaucoma suspect during the screening exam and scheduled for follow-up with an ophthalmologist. This objective outcome variable will be assessed through record review by the study coordinator who is masked to the treatment allocation.

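### The Aim 3 primary outcome has a six-month window in its definition but a three-month window in the Specific Aims and the analysis text, and the November 2023 analysis does not say which it used

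*Protocol*

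**What the plan says.** Three places in the Protocol define the Aim 3 primary outcome.

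- Specific Aim/Hypothesis, Aim 3: "The primary outcome is the proportion of participants attending the recommended physician appointments within three months".
- Research design-Intervention, Primary outcome: attendance "within 6 months due to availability in scheduling these appointments", followed by "Six-month adherence will be used as the endpoint for all participants". This section also gives the numerator (those who attended the first visit booked with an ophthalmologist), the denominator (those diagnosed at screening and booked for such a visit) and the assessor (a coordinator who does not know the arm).
- Data Analysis under Aim 3, Primary outcome: "attendance to follow-up appointment with a glaucoma specialist within three months", to be summarised by arm, overall and by site.

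A fourth place uses the outcome. The section Planned Analysis Results Nov. 14, 2023 reports that adherence did not differ between the arms and ends randomisation for that reason. It names no window.

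**The concern.** The two windows sit side by side in current text, and neither is marked as superseded or as secondary. The section that says what will be summarised uses a different window from the section that defines the endpoint. An analyst who follows the Data Analysis text would score some participants opposite to the definition.

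This matters more than usual because arm-level adherence results have already been read and acted on. A reader cannot tell which window produced the finding of no difference. If the choice between windows is still open, it would now be made by people who know the results.

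**Working it through.** The plan gives no figure of its own to reproduce on this point. The check is a comparison of texts and one identity.

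**1. The texts side by side**

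| Protocol section | Window | Provider |
|---|---|---|
| Specific Aim/Hypothesis, Aim 3 | 3 months | physician |
| Research design-Intervention, Primary outcome | 6 months, all participants | ophthalmologist |
| Data Analysis (Aim 3), Primary outcome | 3 months | glaucoma specialist |
| Planned Analysis Results Nov. 14, 2023 | not named | not named |

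**2. How one participant is classified**

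| Scheduled visit attended | Six-month text | Three-month texts |
|---|---|---|
| by the end of month 3 | adherent | adherent |
| in months 4-6 | adherent | non-adherent |
| later or never | non-adherent | non-adherent |

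Only the middle row changes.

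**3. Effect on the difference between arms**

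Hold the denominator, provider and start of the window the same under both texts. In each arm let A6 and A3 be the proportions adherent by six and three months, and let L be the share attending in months 4-6. Then A3 = A6 - L. Let D6 and D3 be the differences, intervention minus control:

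D3 = D6 - (L_intervention - L_control)

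- If L is equal in the two arms, D3 = D6. Both proportions fall but the difference is unchanged.
- If L is one point higher in the intervention arm, D3 = D6 - 1 point. At the planned 400 randomised 1:1, each arm has 400/2 = 200, so one point is 0.01 × 200 = 2 participants.

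The documents give neither L nor the number actually randomised, so the shift has no computable size or direction. Equality of L cannot simply be assumed. Both arms get a reminder call, but only the intervention arm gets the further counselling call aimed at attendance.

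**4. Dating the six-month sentence**

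The sentence carries no date. Other changes do, including one of March 2024 for Spanish-speaking participants in the Aim 3 overall strategy. The current text as a whole is therefore later than the analysis of 14 November 2023. That does not show when the six-month sentence was written.

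**5. Start of the window**

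No section says where the count begins. Under Follow-up, "The technician will schedule a follow-up visit 4-8 weeks later", and under Block randomization, "The time of randomization is when the patient returns for their follow-up visit with the ophthalmic technician". A count from screening and a count from randomisation therefore differ by 4-8 weeks. The aligned definition should name one start.

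**The case against.** The strongest reply is that this is an incomplete edit. The six-month section gives an operational reason, applies the window to everyone, and is the only place with a full numerator and denominator. A sensible reader would take it as governing. That stands as the most natural reading, and the fix follows it. It does not remove the conflict, because the analysis text still says three months and the November 2023 report names neither.

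Four stronger inferences are tempting, and the documents do not support them.

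- *The window was lengthened after results were seen.* The stated reason is scheduling, most of the protocol is undated, and a March 2024 edit elsewhere does not date this sentence. The document cannot exclude a later change, but it does not show one. A request for the date is fair; an allegation is not.
- *Many recommended visits fall due after three months by design.* The reading physician sets the timing ("A time frame for an in-person ophthalmologist examination will be requested if needed"), but the protocol gives no distribution of those time frames. The clause "the recommended follow up time period is one year or more, will not be randomized" belongs to a sentence about ocular hypertension that also covers low-risk cases and sends them for the principal investigator's review. It does not show that all shorter periods are randomised. If they were, a visit recommended at 7-11 months would fail the six-month window too.
- *Three months was out of reach for many Hope participants because that clinic's sessions run every two months.* This needs a window counted from screening, evenly spaced sessions and no other route to an examination. Counted from randomisation it disappears, since three months is longer than the two-month cycle. It also says nothing about the difference between arms.
- *The specialist wording excludes people seen by the comprehensive ophthalmologist to whom they were referred.* This is probably loose wording and needs only a minor alignment.

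**Conclusion.** The contradiction is real and lies in the primary outcome of the randomised comparison. Every scheduled visit attended in months 4-6 changes category between the two windows. The arm difference changes by exactly the imbalance between arms in such visits, and not at all if there is none. That result assumes the same denominator, provider and start of window under both texts. The 2-of-200 conversion also assumes that the planned 400 were randomised. The actual shift cannot be obtained from the protocol.

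The six-month definition is probably the intended one. What remains unknown is when it was adopted and whether it was the window behind the decision to stop randomising. Until both are stated, the reported lack of difference cannot be tied to a defined endpoint.

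**What to change.** The order matters: establish the history before changing the text.

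1. State which window, and which provider definition, the November 2023 analysis used. State the date on which six months was adopted relative to that analysis.
2. Align the Aim 3 paragraph of the Specific Aims and the Aim 3 Data Analysis text with the definition under Research design-Intervention: six months, an ophthalmologist, and that section's numerator and denominator. Name one start for the window.
3. Report three-month attendance by arm as a labelled supplementary result.
4. If the November 2023 analysis used three months, or six months was adopted after results were seen, say so and report both windows with equal prominence.

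The cost is wording in two sections, one dated statement and, at most, one further two-arm comparison on data already held. No new data collection is needed.

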## Planned Analysis Results Nov. 14, 2023

A planned analysis reported no difference in adherence between the intervention (personal coaching) and the control (standard education). Therefore, we will no longer randomize glaucoma/glaucoma suspect participants and instead ask them to choose which education they would like to receive.

**Follow-up surveys:** All returning participants will complete a satisfaction survey. The intervention group will also be asked to complete; 1) National Eye Institute Glaucoma Eye-Q test, 2) Satisfaction with Information Scale, 3) Clinician and Group Survey of the Consumer Assessment of Healthcare Providers and Systems (CG- CAHPS), 4) Health-Care Climate- eye care (HCCQ), 5) Confidence in question asking, which will be assessed with the following question "How confident are you in your ability to know what questions to ask the ophthalmologist?" and will have responses ranging from 1-10 on a Likert scale where 1 is "not confident at all" and 10 is "extremely confident."

Follow-up Care with an Ophthalmologist: The ophthalmologists who remotely reviews the screening examination data will make recommendations follow-up care. All patients who screen positive for ophthalmic disease will be referred to the comprehensive ophthalmologist at the Hamilton Clinic, or to the Hope-Kellogg ophthalmology clinic that runs every two months on a Saturday. The comprehensive ophthalmologists will either provide definitive care or provide a referral for further sub-specialty care. If the patient has barriers to accessing sub-specialty care at the Hamilton clinic, social workers and financial counselors will be involved to help with logistical barriers. If a patient from Hamilton clinic

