has moderate or severe glaucoma, they can be referred to see the glaucoma specialist from UM who will have one day of clinic per month at Hamilton Clinic. If a patient from Hope requires further specialty consultation or surgery, they will sign up for MSupport, the UM charity care program, with the financial counselor available on-site during the Saturday clinics. Once a patient receives MSupport, they receive free care and medications at the UM for 12 months with the option to renew the services annually with proof of low income. Once a patient receives MSupport, they will be scheduled with the appropriate provider at the UM. For participants that are glaucoma/glaucoma suspect and seen at Hamilton or the Kellogg Eye Center for their follow up exam, these findings and visual field data will be collected and entered into the REDCap database.

One-Year Vision Outcomes: Repeat screenings at one year following the participants initial enrollment will take place during the second and third year of the program, where phone calls will be made to participants screened in the first or second year of the program (regardless if they screened positive or negative for disease) to encourage them to return for a second screening. When they return, they will follow the same protocol as described for the initial visits with the ophthalmic technician above. Although, One-Year visit survey data will only include demographics and the VFQ-9 and Falls survey which they also completed in their initial enrollment. Participants who were already randomized to the clinical trial in Aim 3 will not be re-randomized.

**Two-Year Vision Outcomes**: Repeat screenings will take place during the third year of the program, where phone calls will be made to all participants screened in the first year (regardless if they screened positive or negative for disease) to encourage them to return for a second screening. When they return, they will follow the same protocol as described for the initial visits with the ophthalmic technician above. Participants who were already randomized to the clinical trial in Aim 3 will not be re-randomized.

Participants that do not return to the clinic for a repeat screening examination, will be asked to complete the VFQ-9 survey over the phone when they are contacted.

One and Two-Year Vision Outcomes: These participants will need to meet the inclusion/exclusion criteria listed in section Recruitment Section of this protocol.

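### Aim 3's analysis text names a glaucoma-specialist visit within three months as the primary outcome, in conflict with the protocol's outcome definition and its referral pathway

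*Protocol*

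**What the plan says.** The Protocol states the Aim 3 primary outcome in three places.

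- **Specific Aim/Hypothesis, Aim 3:** "The primary outcome is the proportion of participants attending the recommended physician appointments within three months".
- **Research design-Intervention, Primary outcome:** "adherence to the recommended follow-up appointment with the ophthalmologist within 6 months". The numerator is patients who "attended the initial scheduled follow-up visit with an ophthalmologist as recommended". The denominator is patients given a glaucoma or glaucoma suspect diagnosis at screening and scheduled for ophthalmology follow-up. Ascertainment is by record review by a masked coordinator. On the window it adds: "Six-month adherence will be used as the endpoint for all participants".
- **Data Analysis (Aim 3), Primary outcome:** "attendance to follow-up appointment with a glaucoma specialist within three months", to be summarised by arm, overall and by site.

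The referral pathway is in the paragraph on follow-up care with an ophthalmologist, under Planned Analysis Results Nov. 14, 2023. It begins "All patients who screen positive for ophthalmic disease will be referred to the comprehensive ophthalmologist at the Hamilton Clinic" and gives the Hope-Kellogg Saturday clinic as the alternative. It continues: "The comprehensive ophthalmologists will either provide definitive care or provide a referral for further sub-specialty care". At Hamilton, if a patient "has moderate or severe glaucoma, they can be referred to see the glaucoma specialist from UM who will have one day of clinic per month". Hope patients who need further specialty consultation first enrol in the university's charity-care programme.

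**The concern.** The Data Analysis wording differs from the outcome definition on two elements: who is seen and by when. The provider is not a loose synonym, because the protocol itself separates comprehensive ophthalmologists from the glaucoma specialist and places the specialist after, or apart from, the first referral. A glaucoma suspect who attends the recommended comprehensive visit on time meets the outcome definition and fails the Data Analysis wording.

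This is the primary endpoint of the randomised comparison, and no sentence says which text prevails. The protocol also records that a planned analysis found no difference in adherence and that randomisation was stopped for that reason. It does not say which visit, or which window, counted as adherence in that analysis.

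**Working it through.** **1. The texts side by side**

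| Place in the Protocol | Visit counted | Window |
|---|---|---|
| Specific Aim 3 | recommended physician appointments | 3 months |
| Aim 3 overall strategy (who is randomised) | in-person examination with an ophthalmologist | none given |
| Research design-Intervention, Primary outcome | initial scheduled visit with an ophthalmologist | 6 months, for all |
| Data Analysis, Aim 3 | glaucoma specialist | 3 months |

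A glaucoma specialist is the endpoint provider in one place only. The three-month window appears in two places, against one explicit statement of six months.

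**2. What a literal reading of Data Analysis would do**

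Let p be the true proportion attending the recommended visit. Let s be the share of attended visits that are with a glaucoma specialist. The recorded proportion is then p × s. Under the outcome definition, s plays no part.

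The protocol gives n = 400 and 1:1 allocation, so 200 per arm. It gives no adherence rates, alpha, power or value of s, so there is no stated figure to reproduce. The values of p and s below are assumptions, as is two-sided alpha of 0.05, and s is taken as equal in both arms.

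Power ≈ Φ{ [ |p2 − p1| − 1.96 √(2 p̄(1 − p̄)/n) ] / √([p1(1 − p1) + p2(1 − p2)]/n) }, with p̄ the mean of p1 and p2, and n = 200.

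- 50% v 65%, s = 1: (0.15 − 1.96 × 0.0494)/0.0489 = 1.09, so power is 86%.
- 50% v 65%, s = 0.5: recorded rates are 25% v 32.5%. (0.075 − 1.96 × 0.0453)/0.0451 = −0.30, so power is 38%.

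| Assumed true rates | s = 1 | s = 0.5 | s = 0.25 |
|---|---|---|---|
| 50% v 65% | 86.1% | 38.1% | 18.6% |
| 60% v 74% | 84.8% | 31.6% | 15.3% |
| 70% v 82% | 80.5% | 23.4% | 11.6% |

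**3. Why s cannot be bounded from the protocol**

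In the two earlier programmes cited under Background and Significance, suspects were 21/(17 + 21) = 55% and 23/(19 + 23) = 55% of those found with glaucoma or suspected glaucoma. Those figures come from other cities. The protocol says that moderate or severe patients may be sent to the specialist, but no rule excludes others. It also does not say whether any Hope-Kellogg clinician is a glaucoma specialist.

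Even with assumed inputs the range is wide. Suppose 60% attend overall and 25% are referred to a specialist. If attendance is independent of referral type, the recorded rate is 0.60 × 0.25 = 15%. If every specialist-referred patient attends, it is 25%. If none does, it is 0%.

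**The case against.** The strongest reply is that the outcome definition is the operative text. It gives the numerator, denominator, window and method of ascertainment, while the Data Analysis wording is a parenthesis in a sentence about frequencies and percentages. The rest of the protocol speaks of a physician or an ophthalmologist. Follow-up findings are collected for glaucoma and suspect participants seen at Hamilton or the Kellogg Eye Center, without regard to subspecialty. On this view the parenthesis is stale wording, and a statistical analysis plan that is not shown may settle the matter.

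Much of this stands. A reader might infer that patients who followed the recommendation would be, or were, scored non-adherent. The document does not show that: mis-scoring follows only if the parenthesis is applied in place of the fuller definition.

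A reader might also infer that the endpoint could not test the Aim 3 hypothesis. That does not follow either. Allocation is 1:1 and stratified by clinic, so severity and specialist access should balance between arms within each site. The harm would be dilution and lost power, not a biased comparison of arms.

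What the reply does not remove is the contradiction. The parenthesis sits in the only Aim 3 analysis text in the protocol, nothing subordinates it to the definition, and its three-month window is repeated in the Specific Aim.

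**Conclusion.** The protocol holds conflicting statements of the Aim 3 primary endpoint. They differ on provider (one text against the others) and on window (two texts against one). Applied literally, the Data Analysis wording would leave out patients who kept the recommended comprehensive visit. It would lower the event rate and power, and tie the by-site summary partly to specialist access, which is arranged differently at Hamilton and Hope.

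The size cannot be derived from the protocol. The power figures above only illustrate a mechanism, and they rest on assumed attendance rates, an assumed specialist share equal in both arms, 200 per arm and two-sided alpha of 0.05.

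It is tempting to attribute the null result of November 2023 to the specialist wording. The documents do not support this, because they do not say which definition was used. For the same reason, a reader cannot confirm from the protocol that the result rests on the fuller definition, so the point still matters although randomisation has ended.

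**What to change.** 1. In the Aim 3 Data Analysis section, replace the parenthesis with the event in the outcome definition: attendance at the recommended in-person examination with an ophthalmologist, whatever the subspecialty.
2. In the same edit, reconcile the window across the Specific Aim, the outcome definition and Data Analysis. The outcome definition is the only text that says its window applies to all participants, and it gives appointment availability as the reason.
3. State which visit and which window the November 2023 planned analysis used. If it did not use the reconciled definition, report the result under that definition as well.
4. If specialist attendance is of interest, report it separately among patients referred to a specialist.

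The cost is a sentence or two of protocol text and a statement about an analysis already done. The outcome is already assessed by record review, so no new data stream should be needed. A re-run is needed only if the planned analysis used a different definition. No referral rule or patient management changes.
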